### 9.3.2. Analysis of Secondary Endpoints

All secondary PRO and efficacy endpoints will be based on the FAS unless stated otherwise.

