#### **3.2. Secondary Endpoints**

##### **3.2.1. Efficacy Endpoints**

Secondary efficacy endpoints will be summarized based on data up to initiation of a new anti-cancer drug therapy, if applicable.

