### **4.1. Full Analysis Set**

The Full Analysis (FA) set will include all randomized subjects. Subjects will be classified according to the treatment assigned at randomization.

Randomized but not treated patients will be reported under their randomized treatment group for the full analysis set. The FA set will be the primary population for evaluating all efficacy and PRO endpoints CCI [REDACTED] and patient characteristics.

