### 5.2.9. Analyses for Categorical Data

Qualitative variables will be summarized by frequency counts and percentages. Unless otherwise specified, the calculation of proportions will include the missing category. Therefore counts of missing observations will be included in the denominator and presented as a separate category.

In case the analysis refers only to certain visits, percentages will be based on the number of patients with an assessment at that visit, unless otherwise specified.

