## 6.2. Secondary Endpoints

### 6.2.1. Fatigue

The “Fatigue” single-item from the MDASI-AML/MDS questionnaire is the key secondary endpoint. Similar to analysis of the primary endpoint, the analysis of Fatigue will be conducted separately and independently across the two patient populations (intensive or non-intensive patients). There are two steps of the analysis of Fatigue. If the primary endpoint of OS is met in one population, the hypothesis testing described in Step 2 of this section will be carried out in that population. The overall Type I error is preserved by following this pre-specified hierarchical testing sequence (ie, OS followed by Fatigue).

**Step 1:** A repeated measures model will be used to determine Clinically Important Responder (CIR) within each patient population. We use the change in Fatigue from baseline as the outcome and SGIC-S (Subject Global Impression of Change using PGIS) score (defined below) as the anchor. Note that Fatigue and PGIS are collected following the same schedule and treatment assignment is not a covariate in the model. All available post-baseline data up to Week X will be used (X=8 for intensive patients, X=12 for non-intensive patients). A window of +/-3 days will be applied. If more than one assessment are available in a week, the average value will be used.

A SGIC-S score with three possible values (-1, 0, and 1, treated as continuous variable) will be derived for each subject at each week post-baseline, from Week 1 through Week X, as follows:

- a. SGIC-S = -1, if post-baseline PGIS minus PGIS at baseline is positive (this means *worse*);
- b. SGIC-S = 0, if post-baseline PGIS minus PGIS at baseline is zero (ie, no change, this means *the same*);
- c. SGIC-S = 1, if post-baseline PGIS minus PGIS at baseline is negative (this means *better*).

The predicted change in Fatigue score corresponding to one unit difference on SGIC-S is the threshold for “responder” vs “non-responder”. All patients with change in Fatigue at Week X (X=8 for intensive patients, X=12 for non-intensive patients) at or below the threshold (note that lower values suggest lessening of Fatigue) will be defined as responders.

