As a supportive analysis, a SGIC-C (Subject Global Impression of Change using PGIC) score with three possible values (-1, 0, and 1, treated as continuous variable), derived below, will be used in place of SGIC-S in the repeated measures model. Note that PGIC is collected on the same schedule as Fatigue other than there is no assessment of PGIC at baseline.

- a. SGIC-C = -1, if PGIC is 5 or more (this means *worse*);
- b. SGIC-C = 0, if PGIC is 4 (ie, no change, this means *the same*);
- c. SGIC-C = 1, if PGIC is 3 or less (this means *better*).

Additional details of the CIR can be found in the Appendix, where potential sensitivity analyses treating SGIC-S and SGIC-C as categorical variables are also described.

**Step 2:** A formal testing of proportion of responders at Week X (using a 1-sided Cochran Mantel Haenszel [CMH] test, stratified by ELN risk, age [age  $\leq 60$  vs  $>60$  years for the intensive patients, and age  $<75$  vs  $\geq 75$  years for the non-intensive patients], and region [ROW vs China for intensive patients only) will only be conducted in one population if the primary OS endpoint is met in that population (intensive or non-intensive patients). The risk ratio and 2-sided 95% CI will be summarized.

The proportion of responders by treatment arm will be estimated with a 2-sided 95% CI (using normal approximation). The proportion and 2-sided 95% CI (using exact method) of responders for each stratum by treatment arm will also be provided.

In addition to the above responder analyses, analysis of Fatigue will also be supplemented with cumulative distribution function (CDF) and probability density function (PDF) of change in Fatigue score from baseline to Week X. The change in Fatigue at Week X will be plotted on the X-axis while its CDF or PDF will be plotted on the Y-axis.

If the Week X PRO assessment is missing, then the next available completed PRO assessment will be used.

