#### **6.2.6. Patient-Reported Outcomes**

All PRO analyses will be based on the FA **CCI** [REDACTED].

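### A missing Week 8/12 Fatigue score is replaced by the next completed questionnaire, forward only and with no maximum interval, in the only test after OS

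*SAP*

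**What the plan says.** SAP 6.2.1 makes the single MDASI-AML/MDS Fatigue item the key secondary endpoint. It is tested by a 1-sided stratified CMH test within each study, only if OS is met there. The responder definition covers "All patients with change in Fatigue at Week X", with X = 8 (intensive) or 12 (non-intensive). The weekly data in Step 1 carry a visit window: "A window of +/-3 days will be applied". The section ends with the rule for a missing score: "If the Week X PRO assessment is missing, then the next available completed PRO assessment will be used".

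Two other places limit the data. SAP 3.2.1 says "Secondary efficacy endpoints will be summarized based on data up to initiation of a new anti-cancer drug therapy, if applicable", and SAP section 2 sets a data cutoff driven by OS events. Neither ties a substituted score to Week X.

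The protocol's schedule fixes what the next questionnaire can be. In the non-intensive study it is completed on Days 1, 7 and 15 of Cycle 1, on Day 1 of each later cycle and at end of treatment (Table 3, footnote 22). The end-of-treatment visit falls within 14 days of last dose, and later visits are every 3 months from last dose (footnotes 27 and 28). Table 1, footnotes 24, 29 and 30, set the same post-treatment pattern for the intensive study. The contact at 28 to 35 days is for adverse events and contraception and may be a phone call (Protocol 6.4).

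**The concern.** A score taken months after Week X, from a patient long off treatment, does not measure fatigue at Week X. The rule prefers such a score to one taken days before the target, because it never looks back. A late score also exists only for patients who live to give it. Fatigue is the only endpoint after OS in the formal testing sequence, so the rule helps decide a confirmatory result.

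**Working it through.** The visible documents give no sample size, response rate or completion rate for Fatigue, so there is no figure of the plan's own to reproduce. The check uses the schedule first and then a model for frequency.

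**1. Length of the delay (non-intensive).** Week 12 is Day 1 + 84 = Day 85. I assume that the ±3-day window defines the visit (Days 82-88); ±7 days (Days 78-92) leaves the Day 63 case unchanged. With last dose on Day d, the end-of-treatment score comes by d + 14 and the next scheduled one at about d + 91.

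| Last dose | End-of-treatment score by | Days before 85 | Next scheduled score | Days after 85 |
|---|---|---|---|---|
| Day 43 | Day 57 | 28 | Day 134 | 49 |
| Day 63 | Day 77 | 8 | Day 154 | 69 |
| Day 67 | Day 81 | 4 | Day 158 | 73 |

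In each row the rule skips the nearer score and uses the later one. If the 3-month score is also missed, the rule moves on to the one after it. The table takes the end-of-treatment visit at the end of its allowance. With last dose on Day 43 and the visit on Day 44, the comparison is 41 days early against 49 days late, which is much closer.

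**2. How often (assumption).** The only time-on-treatment figure found is a median of 94.0 days in the azacitidine-glasdegib lead-in cohort (Protocol Summary; 12 patients with MDS, AML or CMML). I take exponential time on treatment, P(T > t) = 0.5^(t/median), and a median of 180 days as an alternative.

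- Last dose on Days 43-67, median 94: 0.5^(42/94) − 0.5^(67/94) = 0.734 − 0.610 = 0.124, about 20 of 160 per arm.
- Median 180: 0.5^(42/180) − 0.5^(67/180) = 0.851 − 0.773 = 0.078, about 12 of 160.

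For that range of last doses these are upper bounds. They include patients who stop because they die, and patients who start a new drug and are cut off by SAP 3.2.1. No comparable figure is available for the intensive study.

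**3. Dependence on survival.** SAP 5.1.1 assumes exponential OS with medians of 10.4 and 16.2 months; a month is 30.4375 days. The probability of dying in the 69 days from Day 85 to Day 154 is 1 − 0.5^(69/(30.4375 × 10.4)) = 0.140 for control and 1 − 0.5^(69/(30.4375 × 16.2)) = 0.092 for glasdegib.

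**4. What a ±28-day window would leave empty.** For Week 12 the window is Days 57-113.

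- End-of-treatment score at d + 14: last doses on Days 23-42 have none in the window (end of treatment Days 37-56, next score Days 114-133). Probability 0.850 − 0.734 = 0.117 at a 94-day median and 0.919 − 0.851 = 0.068 at 180 days (differences taken before rounding).
- End-of-treatment score the day after last dose: Days 23-55 have none. Probability 0.850 − 0.667 = 0.184 and 0.919 − 0.809 = 0.110.

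Both are before removing deaths and new-drug starts.

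**5. Denominator.** SAP 5.2.9 first says that missing observations count in the denominator, and then, for visit-specific analyses, that "percentages will be based on the number of patients with an assessment at that visit, unless otherwise specified". SAP 4.1 says "The FA set will be the primary population for evaluating all efficacy and PRO endpoints" and Protocol 9.3.2 says "All secondary PRO and efficacy endpoints will be based on the FAS unless stated otherwise". Under the plan's medians, deaths by Week 12 are 16.8% (control) and 11.1% (glasdegib), so if deaths are the only missing values the choice moves the risk ratio by 0.889/0.832 = 1.07. At Week 8 in the intensive study, 5.9% and 4.0% give 0.960/0.941 = 1.02.

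**The case against.** The rule is pre-specified and neutral between arms in its wording. What is shown is a delay, not a bias. The frequency rests on a small mixed cohort and an assumed distribution, and the clearest example puts the end-of-treatment visit late in its allowance. All of this stands, and it limits the size of the claim. It does not remove the defect, because the SAP as written requires the late score to be used.

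The missing-score sentence follows the paragraph on distribution plots, so its use in the CMH test is the natural reading but not an explicit one. If it covered only the plots, the test would fall back on the as-observed default in SAP 5.3, and that too should be stated.

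Redaction is a real limit. A heading at the end of SAP 5.3 and an analysis set in SAP 4.4 are blacked out, and the sentence in SAP 6.2.6 that begins "All PRO analyses will be based on the FA" breaks off. The COVID-19 sensitivity analyses listed in SAP Table 1 are not visible either, but as sensitivity analyses they would not replace the main rule.

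A reader might infer that the denominator is left open. The documents do not support that. The first part of SAP 5.2.9, SAP 4.1, Protocol 9.3.2 and the visible part of SAP 6.2.6 all point to the full analysis set, and the visit rule gives way where something else is specified. One confirming line is enough.

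A reader might also infer that death and new therapy must be written in as non-response in the prescribed test. That is a choice of estimand and has its own cost. If survivors in both non-intensive arms respond at an assumed 35%, counting deaths as non-response gives rates of 0.291 and 0.311. With 160 per arm and an unstratified normal approximation, the chance of 1-sided p < 0.025 is then about 5.8%.

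**Conclusion.** The point holds for the substitution rule. It is forward only and has no maximum interval in the visible text, apart from the stops at a new anti-cancer drug and the data cutoff. After early discontinuation in the non-intensive study, a score 49 to 73 days late can stand for Week 12 while one 4 to 28 days early is ignored. These ranges assume last doses on Days 43-67, an end-of-treatment visit at 14 days and a ±3-day visit window. The share of patients is unknown; 8% to 12% is a modelled upper bound for that range of last doses.

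A reader might go further and infer that the rule favours glasdegib. The documents do not show this. The direction and size of any effect depend on how many patients in each arm stop early, survive and have a different score later, and none of these is given. The denominator needs confirming but is not a defect of the same weight. The rule should be fixed before unblinding.

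**What to change.** In SAP 6.2.1, replace the next available score with the completed questionnaire nearest to Week X within a stated two-sided maximum interval, before any new anti-cancer drug, with a rule for ties. An interval of ±28 days is one example (Days 57-113 for Week 12, Days 29-85 for Week 8). State that the rule applies to the CMH test, and report by arm how many patients have no value in the window.

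As a clarification, add a line that the responder proportion uses the full analysis set rather than the visit rule in SAP 5.2.9, and add a sensitivity analysis in assessed patients only.

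The cost is SAP wording and programming. There are two downsides. A score up to 28 days early or late can stand for Week X. Some early discontinuers will have no scheduled questionnaire in the window: in the non-intensive study about 12% to 18% at a 94-day treatment median and 7% to 11% at 180 days, depending on when the end-of-treatment visit falls, before removing deaths and new-drug starts. Patients still on treatment are not guaranteed a value either. The 28-day limit on cycle delay in Protocol 5.5.1.3 is for blood-count recovery, while Table 3 (footnotes 13 and 14) and Table 8 (footnote a) allow extension for toxicity with no cap stated there.

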### 6.2.2. Responses

The proportion of patients achieving CRMRD-negative, CR (including CRMRD-negative), CRi, CRh (non-intensive only), MLFS, and PR as their best overall response will be estimated with two-sided 95% CI (using normal approximation). The proportion and two-sided 95% CI (using exact method) of patients achieving each response category for each stratum will also be provided. The proportion of patients with CRMRD-negative, CR (including CRMRD-negative), CRi or better and CRh or better (non-intensive only) respectively will be compared between the 2 treatment arms using a 1-sided CMH stratified test and an unstratified chi-square test. The risk ratio and difference in proportions and their 95% CIs will be provided overall and within each stratum as well. The proportion of patients experiencing stable disease, indeterminate response (eg, those that met the criteria for stable disease but for <3 months in the non-intensive study or those where response could never be assessed due to missing information such as peripheral or bone marrow blasts) and disease progression as their best response or ever experiencing disease progression will also be summarized. For those patients not assessed for response, the reason for treatment discontinuation will be summarized. Patients with indeterminate as their best response will be categorized into one of the following groups: no post-baseline bone marrow blasts available, post-baseline bone marrow blasts available but missing peripheral blood data, stable disease for <3 months in the non-intensive study, or other. Patients without a response CRF will be classified as Not Evaluated and the overall reason for discontinuation from treatment will be summarized.

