### **Disease Specific Efficacy Endpoints**

Disease specific efficacy endpoints include CR, CRMRD-neg (a subgroup of CR), Complete remission with incomplete hematologic recovery (CRi), Complete remission with partial hematologic recovery (CRh, only defined for Non-intensive patients), Morphological Leukemia Free State (MLFS), and Partial Remission, as defined according to the 2017 ELN recommendations. Note that CR (including CRMRD-neg) is always a deeper response than CRi. CR (including CRMRD-neg) is a deeper response than CRh (if applicable), and CRh (if applicable) is a deeper response than CRi.

The proportion of subjects achieving each endpoint will be estimated with 2-sided 95% CI (using the normal approximation) respectively. The proportion and 2-sided 95% CI of subjects achieving each of the endpoint for each stratum will also be provided. The proportion of subjects achieving each endpoint will be compared between the treatment arms using a 1-sided CMH stratified test (stratified as described in [Section 9.3.1](#)) and an unstratified chi-square test.

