## 2.2. Study Design

Two separate registration trials conducted under one protocol number are proposed to adequately and independently evaluate the addition of glasdegib in intensive and non-intensive chemotherapy populations. Each study will have an experimental treatment arm and a placebo arm.

Study B1371019 (Figure 1) is a randomized (1:1), double-blind, multi-center, placebo controlled study of chemotherapy in combination with glasdegib versus chemotherapy in combination with placebo in adult patients with previously untreated AML (excluding APL with PML-RARA, AML with BCR-ABL1 and active central nervous system [CNS] leukemia) to support the proposed indication statements:

- Intensive Study: Glasdegib is being studied in combination with cytarabine and daunorubicin for the treatment of adult patients with untreated AML.
- Non-intensive Study: Glasdegib is being studied in combination with azacitidine for the treatment of adult patients with untreated AML who are not candidates for intensive induction chemotherapy.

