#### Intensive Chemotherapy Study:

The primary objective of the study is to demonstrate that glasdegib in combination with 7+3 (Arm A) is superior to placebo in combination with 7+3 (Arm B) in prolonging OS.

The study is designed to test  $H_0: HR \geq 1$  vs.  $H_A: HR < 1$ , where HR is the hazard ratio (Arm A/Arm B) of OS.

A total of 400 subjects eligible to receive intensive chemotherapy per investigator assessment will be enrolled into the study. A total of 267 death events to be observed in the study would provide 90% power to detect an improvement in overall survival translated in mOS from 21 months to 31.5 months assuming a composite mOS for the population as follows: young AML (aged  $\leq 60$  years) with a mOS of 23.7 months and elderly AML (aged  $> 60$  years) with a mOS of 15 months assuming a 70% young and 30% elderly AML split and with an  $HR=0.67$  using a 1-sided log-rank test at a significance level of 0.025 and a 3-look group-sequential design.

The sample size of 400 subjects is determined based on the assumption of a HR of 0.67 under the alternative hypothesis (under an exponential model, translating in median OS of 31.5 months in the treatment arm and 21 months in the control arm) expecting approximately one third of all enrolled subjects to be censored. It is assumed a ramping enrollment of 10 months to reach a maximum enrollment of 18 patients/month. An accrual duration of 28 months to randomize 400 patients and an overall trial duration of 58 months is expected.

For the China subset, no formal statistical testing will be conducted.

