#### **Non-Intensive Chemotherapy Study:**

The primary objective of the study is to demonstrate that glasdegib in combination with azacitidine (Arm A) is superior to placebo in combination with azacitidine (Arm B) in prolonging OS.

The study is designed to test  $H_0: HR \geq 1$  vs.  $H_A: HR < 1$ , where HR is the hazard ratio (Arm A/Arm B) of OS.

A total of 320 subjects who are not candidates to receive Intensive Chemotherapy will be enrolled into the study. A total of 220 death events to be observed in the study would provide 90% power to detect an improvement in overall survival translated in mOS from 10.4 months to 16.2 months with an  $HR=0.64$  using a 1-sided log-rank test at a significance level of 0.025 and a 2-look group-sequential design. One interim efficacy and futility analysis of OS would be planned after 60% death events occur in the non-intensive chemotherapy population or upon completion of enrollment of these subjects, whichever is later.

The sample size of 320 subjects is determined based on the assumption of a HR of 0.64 under the alternative hypothesis (under an exponential model, translating in median OS of 16.2 months in the treatment arm and 10.4 months in the control arm) expecting approximately 31% of all enrolled subjects to be censored. It is assumed a ramping enrollment of 10 months to reach a maximum enrollment of 18 patients/month. An accrual duration of 23 months to randomize 320 patients and an overall trial duration of 37 months is expected.

For the China subset, no formal statistical testing will be conducted.

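### Whole-arm response rates get a normal-approximation 95% CI with no small-count fallback, so coverage can fall below 90% for any category that proves rare

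*SAP*

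**What the plan says.** SAP 6.2.2 covers CR without MRD, CR, CRi, CRh (non-intensive only), MLFS and PR. It says that the proportion of patients with each "as their best overall response will be estimated with two-sided 95% CI (using normal approximation"). Protocol 9.3.2, under the disease-specific endpoints, agrees: "The proportion of subjects achieving each endpoint will be estimated with 2-sided 95% CI (using the normal approximation) respectively".

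The next SAP sentence uses a different method within strata: "The proportion and two-sided 95% CI (using exact method) of patients achieving each response category for each stratum will also be provided". The protocol also asks for stratum intervals but names no method for them.

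The arms are compared by tests, not by these intervals. In the SAP, CR without MRD, CR, CRi or better and CRh or better "respectively will be compared between the 2 treatment arms using a 1-sided CMH stratified test and an unstratified chi-square test".

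The denominator is all randomized patients: "The FA set will be the primary population for evaluating all efficacy and PRO endpoints" (SAP 4.1).

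**The concern.** The Wald interval centres on the observed proportion and takes its width from that same proportion. When few patients respond, the estimated width is too small and the symmetric interval can run below zero. The plan applies this method to every category, including those that count only patients with no deeper response (MLFS and PR, for example), and has no rule for small counts.

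What is at stake is the uncertainty statement printed beside a secondary endpoint. An interval labelled 95% might cover much less often. An arm with no responders would be reported as 0% to 0%, as though the rate were known exactly.

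**Working it through.** The plan states no coverage, precision or expected rate for the response categories, so there is no planned figure to reproduce. The check is how the stated method behaves at the stated arm sizes.

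**Inputs**
- Intensive study: "A total of 400 subjects eligible to receive intensive chemotherapy per investigator assessment will be enrolled into the study" (SAP 5.1.1). Allocation: "Study B1371019 (Figure 1) is a randomized (1:1), double-blind" (SAP 2.2). So n = 400/2 = 200 per arm.
- Non-intensive study: "A total of 320 subjects who are not candidates to receive Intensive Chemotherapy will be enrolled into the study" (SAP 5.1.1). So n = 320/2 = 160 per arm.
- Rates the documents do give. For CR: 15-17% on azacitidine alone and 47% in the single-arm 7+3 plus glasdegib cohort (Protocol Summary, Background and Rationale), and 54% in an earlier trial of intensive chemotherapy in mainly older patients (protocol 1.3.2). For CRi in intensive chemotherapy: 55% - 47% = 8% in the single-arm cohort, and 8% for remission without platelet or neutrophil recovery in the earlier trial.
- Rates for PR, MLFS, CRh and non-intensive CRi are not given. They are treated as unknown over a range from 0.5% upward.

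**Coverage.** For x responders, q = x/n and the Wald interval is q ± 1.96 × sqrt(q(1-q)/n). For a true rate p, coverage is the sum of Binomial(n, p) probabilities over every x whose interval contains p.

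| True rate | n=200 | n=160 |
|---|---|---|
| 0.5% | 63.2% | 55.1% |
| 1% | 86.5% | 79.8% |
| 1.5% | 80.0% | 90.8% |
| 2% | 90.8% | 82.6% |
| 3% | 93.3% | 85.8% |
| 4% | 89.8% | 88.1% |
| 5% | 92.6% | 89.9% |
| 6% | 94.9% | 91.5% |
| 8% | 95.3% | 93.8% |
| 15% | 94.4% | 94.4% |
| 17% | 94.9% | 93.4% |
| 47% | 94.4% | 94.3% |
| 55% | 94.5% | 95.3% |

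Coverage oscillates with p because the data are counts. The highest true rate at which it is below 90% is about 4.0% for n=200 and 5.8% for n=160. Averaged over rates of 2-5%, it is 91.8% (n=200) and 90.8% (n=160), with minima of 85.4% and 82.6%.

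**Impossible or degenerate limits.** The lower limit is negative when q < 1.96 × sqrt(q(1-q)/n), that is, when x < n × 3.84/(n + 3.84). This gives x < 3.77 for n=200 and x < 3.75 for n=160, so it happens with 1, 2 or 3 responders. With x = 0 the width is zero.
- 2 of 160: 1.25% ± 1.96 × sqrt(0.0125 × 0.9875/160) = -0.47% to 2.97%. The exact interval is 0.15% to 4.44%.
- 0 responders: Wald gives 0% to 0%. The exact upper limit is 1 - 0.025^(1/n), which is 1.8% (n=200) or 2.3% (n=160).
- Chance of 0 to 3 responders in an arm: 43% (n=200) or 60% (n=160) at a true rate of 2%, but 0.006% or 0.09% at 8%.

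**Exact method on the same grid.** Clopper-Pearson coverage is 95.3% to 99.1% at every rate checked from 0.5% to 70%, for both arm sizes.

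**China subset.** SAP 5.1.2 has this subset analysed under the specifications of the other sections, and its size is not stated. If it had 40 patients per arm, Wald coverage would be 83.7% at a true rate of 8% and 55.3% at 2%. With 80 per arm it would be 88.0% at 8%. Both sizes are assumptions.

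**The case against.** The strongest case against acting has four parts.

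- **The shortfall is conditional.** A reader might infer that the planned intervals in general cover only 80-90%. The documents do not support that. It needs true rates of roughly 1-5%, which no section states, and even there coverage at n=200 is often above 90%. This stands.
- **CRi is not shown to be rare.** A reader might put it with PR and MLFS. The documents' own figures place it near 8% in intensive chemotherapy, where coverage is 95.3% (n=200) and negative or zero-width limits are practically excluded. This stands for the intensive study. It does not carry over to the non-intensive study, where CRh is a separate category and Appendix 4 of the protocol limits CRi to neutrophils below 0.5 or platelets below 50 × 10⁹/L.
- **Two methods are not a contradiction.** A reader might call the exact stratum intervals and the approximate whole-arm intervals inconsistent. The split is a recognisable convention: exact where counts are smallest, approximate for arms of 160-200. It is used for Fatigue as well (SAP 6.2.1, protocol 9.3.2), and the protocol's Amendment 5 log shows that the interval method was considered. This stands, but the convention does not protect a whole-arm category with few responders.
- **No decision depends on these limits.** The OS test, the Fatigue test that follows it and the stratified response comparisons do not use them. This stands and sets the weight of the point.

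**Conclusion.** The point holds in a limited form. The stated rule gives unreliable limits for any whole-arm response category that turns out rare: below about 4% in the intensive study or 6% in the non-intensive study. In such a category coverage can be 80-90%, or lower still for rates under 1%. Negative or 0% to 0% intervals are possible outcomes there, not certain ones. For CR at the rates the documents cite, and for intensive-study CRi near 8%, the planned interval is sound, with coverage of about 93-95%.

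The conclusion rests on equal arms of the planned size and on assumed rates for PR, MLFS, CRh and non-intensive CRi. In the smaller China subset the weakness would reach higher rates, to an extent that depends on a size the documents do not state. This affects the quality of descriptive reporting and does not threaten any trial conclusion.

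**What to change.** In SAP 6.2.2 and in the disease-specific endpoints part of protocol 9.3.2, replace the normal approximation with the exact (Clopper-Pearson) method for the whole-arm response proportions. This matches what the SAP already specifies by stratum. Name one method rather than offering a choice. It would help to state the stratum method in the protocol sentence too, since it is silent there. Section 9 of the protocol lets the SAP modify such details, so the protocol text can follow at the next amendment.

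The cost is a short wording change and slightly wider, somewhat conservative intervals. For 2 of 160, the width goes from 3.44 points (2.97 + 0.47) to 4.29 points (4.44 - 0.15). No test, alpha or sample size changes. The Fatigue responder proportions use the same approximate-overall, exact-by-stratum split. The sponsor should either align them or say that the response categories are treated differently because some may be rare.
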